### **16.3 REPEATED OR UNSCHEDULED ASSESSMENTS OF SAFETY PARAMETERS**

If a participant has repeated assessments before the start of double-blind treatment with investigational product, the results from the final assessment made before the date of the first dose will be used as baseline. If EOT assessments are repeated or unscheduled, the last post-baseline assessment will be used as the EOT assessment for generating summary statistics.

However, all post-baseline assessments will be used for PCS value determination, and all assessments will be presented in the data listings.

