8.2.4. Clinical Safety Laboratory Assessments

- See [Appendix 2](#) for the list of clinical laboratory tests to be performed and the [Schedule of Activities](#) for the timing and frequency.
- At screening, the Investigator or sub-investigator will assess the clinical significance of any values outside the reference ranges provided by the laboratory, and participants with abnormalities judged to be clinically significant will be excluded from the study.

Armour Thyroid

- The Investigator must review the laboratory report, document this review, and record any clinically relevant changes occurring during the study in the AE section of the eCRF. The laboratory reports must be filed with the source documents. Clinically significant abnormal laboratory findings are those which are not associated with the underlying disease, unless judged by the Investigator to be more severe than expected for the participant's condition.
- All laboratory tests with values considered clinically significant during participation in the study or at the EOS should be repeated until the values return to normal or baseline or are no longer considered clinically significant by the Investigator.
 - If such values do not return to normal/baseline within a period of time judged reasonable by the Investigator, the etiology should be identified, and the Sponsor notified.
 - All protocol-required laboratory assessments, as defined in [Appendix 2](#), must be conducted in accordance with the laboratory manual and the [Schedule of Activities](#).
 - If laboratory values from non-protocol specified laboratory assessments performed at the institution's local laboratory require a change in participant management or are considered clinically significant by the Investigator (eg, SAE or AE or dose modification), then the results must be recorded in the eCRF.
 - Serum pregnancy tests and urine dipsticks are to be used to conduct pregnancy tests by the study personnel or designee at timepoints specified in the Schedule of Activities. Urine dipstick results will be read locally.

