## 11.2

## CLINICAL LABORATORY PARAMETERS

Descriptive statistics for clinical laboratory values (in SI units) at baseline (screening) and changes from baseline at each assessment will be presented by study intervention for each clinical laboratory assessment.

 
Laboratory Assessments
 
		
 
Parameters
 
		
Thyroid-related	
 
Serum TSH, T4, T3, FT4, and FT3
 
			
Thyroglobulin and anti-thyroglobulin	
 
Thyroglobulin and anti-thyroglobulin testing only applicable for participants who have undergone total thyroidectomy for treatment of thyroid cancer
 
			
Hematology	Platelet count	RBC indices: MCV	WBC count with differential (absolute): Neutrophils	
	RBC count	MCH	Lymphocytes	
	Hemoglobin	MCHC	Monocytes	
	Hematocrit	%Reticulocytes	Eosinophils	
			Basophils	
Clinical Chemistry	BUN	Potassium	AST	Total, direct and indirect bilirubin
	Creatinine	Sodium	ALT	Total protein
	Glucose	Calcium	Alkaline phosphatase	Cholesterol, chloride, albumin
	HbA1c			
Routine Urinalysis a	
 
Specific gravity
 
pH, glucose, protein, blood, ketones
 
Microscopic examination (if blood or protein is abnormal)
 
			
Pregnancy Test a	
 
Urine and serum test (females of CBP)
 
			

ALT = alanine aminotransferase; AST = aspartate aminotransferase; BUN = blood urea nitrogen; CBP = childbearing potential; FT3 = free T3; FT4 = free T4; MCH = mean corpuscular hemoglobin; MCHC = mean corpuscular hemoglobin concentration; MCV = mean corpuscular volume; RBC = red blood cell; T3 = liothyronine; T4 = levothyroxine; TSH = thyroid-stimulating hormone; WBC = white blood cell

a Serum pregnancy tests will be standard at the Screening Visit (Visit 1) and Visit 7; local urine testing will be standard for all other visits, as specified in the schedule of activities, unless serum testing is required by local regulation or IRB/IEC.

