#### 2) Participants for 24-week Titration Period Visit Time Windows for Analysis

Derived Visit		Window
Visit 2 Baseline	Day 1	Days $\leq$ 1
Visit 3a Week 6	Day 42	Days [2, 63]
Visit 4a Week 12	Day 84	Days [64, 105]
Visit 5a Week 18	Day 126	Days [106, 147]
Visit 5c Week 24	Day 168	Days [148, last day of TP]
Visit 6 Week 30	Day 210	Days [first day of SP, 231]
Visit 7 Week 36	Day 252	Days $>$ 231

3) Participants for 30-week Titration Period Visit Time Windows for Analysis

Derived Visit		Window
Visit 2 Baseline	Day 1	Days $\leq$ 1
Visit 3a Week 6	Day 42	Days [2, 63]
Visit 4a Week 12	Day 84	Days [64, 105]
Visit 5a Week 18	Day 126	Days [106, 147]
Visit 5c Week 24	Day 168	Days [148, 189]
Visit 5e Week 30	Day 210	Days [190, last day of TP]
Visit 6 Week 36	Day 252	Days [first day of SP, 273]
Visit 7 Week 42	Day 294	Days $>$ 273

4) Participants for 36-week Titration Period Visit Time Windows for Analysis

Derived Visit		Window
Visit 2 Baseline	Day 1	Days $\leq$ 1
Visit 3a Week 6	Day 42	Days [2, 63]
Visit 4a Week 12	Day 84	Days [64, 105]
Visit 5a Week 18	Day 126	Days [106, 147]
Visit 5c Week 24	Day 168	Days [148, 189]
Visit 5e Week 30	Day 210	Days [190, 231]
Visit 5g Week 36	Day 252	Days [232, last day of TP]
Visit 6 Week 42	Day 294	Days [first day of SP, 315]
Visit 7 Week 48	Day 336	Days $>$ 315

TP = Titration Period; SP = Stabilization Period.

Last day of TP is the day of last TSH visit prior to visit 6.

First day of SP is defined as the last day of TP + 1.

If the visit date is on or after the date of the first dose of double-blind study treatment, the study day is calculated by visit date – date of the first dose of double-blind investigational product + 1. If the visit date is before the date of the first dose of double-blind investigational product, the study day is calculated by visit date – date of the first dose of double-blind investigational product. Therefore, a negative day indicates a day before the start of the double blind investigational product.

If a participant has 2 or more visits within the same window, the last visit with a non-missing value will be used for analysis.

The titration visits 5b, 5d, and 5f will be included in the analysis visits 5a, 5c, 5e, or 5g based on the definition of analysis visit window.

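### End-of-trial laboratory summaries can take a resolved repeat in place of the scheduled Visit 7 or Early Termination value, which biases those descriptive statistics toward no change (minor)

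*SAP*

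**What the plan says.** SAP 16.3, which is headed as applying to safety parameters, sets the rule for end-of-trial (EOT) values: "If EOT assessments are repeated or unscheduled, the last post-baseline assessment will be used as the EOT assessment for generating summary statistics". The next sentence limits its reach: "However, all post-baseline assessments will be used for PCS value determination, and all assessments will be presented in the data listings".

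SAP 16.2 has a general rule in the same direction: "If a participant has 2 or more visits within the same window, the last visit with a non-missing value will be used for analysis". Its Visit 7 windows are open-ended: any day after Day 189, 231, 273 or 315, depending on the length of the Titration Period.

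Protocol 8.2.4 governs when laboratory tests are repeated. It covers "All laboratory tests with values considered clinically significant during participation in the study or at the EOS" and says that these "should be repeated until the values return to normal or baseline or are no longer considered clinically significant by the Investigator". It also foresees values that do not resolve: "If such values do not return to normal/baseline within a period of time judged reasonable by the Investigator".

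The affected output is in SAP 11.2, where "changes from baseline at each assessment will be presented by study intervention for each clinical laboratory assessment". SAP 11.0 names the statistics: number of patients, mean, SD, median, minimum and maximum.

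**The concern.** In Protocol 8.2.4 an abnormal result starts the repeats, and recovery is the usual reason to stop. Taking the last member of such a series selects the value by its outcome. A participant whose final scheduled result was clinically significant can enter the EOT table with a later, resolved result.

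The repeat will normally also be off treatment. SAP Table 4-1 shows no dispensing at Visit 7, and Protocol 6.7 provides no intervention after the end of the study. The EOT row would then mix on-treatment values with recovery values.

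The pull is toward no change and is larger in the arm with more abnormalities, so the comparison of arms in these tables can be blunted.

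**Working it through.** There is no stated figure to reproduce: this is a data-handling rule, and no sample size, power or alpha depends on it. The check sets the rules side by side and then gives an illustration.

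**1. Final visit.** Suppose a clinically significant laboratory value at Visit 7 is repeated later and resolves. The repeat still lies in the Visit 7 window, because that window never closes. SAP 16.3 makes it the EOT value, and SAP 16.2 would pick it as well. Neither rule limits how late it may be.

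**2. Earlier visits.** Substitution needs the repeat to fall in the same window.
- Visit 3a covers Days 2 to 63. A repeat on Day 50 replaces a Day 42 value. A repeat on Day 70 falls in the Visit 4a window (Days 64 to 105), where the later scheduled Visit 4a value supersedes it.
- The visit that ends titration has a window closing on the last day of that period, defined as the day of the last TSH visit before Visit 6. If that is Day 126, a liver-enzyme-only repeat on Day 130 falls in the Visit 6 window, and the abnormal end-of-titration value stays in its own summary.

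**3. Which outputs change.**

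| Output | Value used | Affected? |
|---|---|---|
| EOT mean, maximum, change from baseline (SAP 11.0, 11.2) | last repeat | yes |
| PCS counts (SAP 11.2, 16.3) | any post-baseline value | no |
| Hy's Law without time window (SAP 11.5.2) | post-baseline maximum | no |
| Adverse event tables (SAP 11.1) | event record | no |
| Listings (SAP 16.3) | all values | no |

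**4. Illustration.** From the SAP: 142 participants per arm (4.1) and the ALT limit of at least 3 × ULN (Table 11-1). Assumed, not in the documents: other participants at 0.5 × ULN, *k* participants with an abnormal scheduled final ALT, and every repeat settling at 1 × ULN.

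Fall in arm mean = *k* × (scheduled − repeat) / 142.

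| *k* | Scheduled value | Calculation | Fall in mean (× ULN) | PCS count |
|---|---|---|---|---|
| 1 | 2 × ULN | 1 × (2 − 1) / 142 | 0.007 | 0 |
| 5 | 3 × ULN | 5 × (3 − 1) / 142 | 0.070 | 5 |
| 10 | 2 × ULN | 10 × (2 − 1) / 142 | 0.070 | 0 |
| 10 | 5 × ULN | 10 × (5 − 1) / 142 | 0.282 | 10 |

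The PCS count is the same whichever value is summarised, because it already uses all values. The third row shows the real gap: ten participants at 2 × ULN leave the EOT summary and are not PCS either.

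**5. Parameters without a PCS limit.** SAP 11.2 lists TSH, T4, T3, FT4, FT3 and HbA1c as laboratory parameters, but Table 11-1 gives no criterion for any of them. In the readable text of SAP 11.2, descriptive statistics are their only tabulated laboratory summary.

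**The case against.** A reader might infer that every abnormal final value is swapped for a normal one and that a safety difference could disappear from the report. The documents do not support this.

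- **Normalization is not guaranteed.** Repeats may stop at baseline level or when the investigator no longer judges the value significant, and Protocol 8.2.4 expects some not to resolve. The last value can still be abnormal.
- **Abnormality is not the only trigger.** The opening bullets of Protocol Section 8 also allow repeats for technical problems with samples. Those do not depend on the result, but they do not cancel the repeats that do.
- **The abnormality is kept elsewhere.** PCS counts, Hy's Law maxima and listings hold it. Protocol 8.2.4 also has investigators "record any clinically relevant changes occurring during the study in the AE section of the eCRF". In the illustration, everyone at or above 3 × ULN remains in the PCS table.
- **Scope is narrower than SAP 16.3 suggests.** The repeat order covers laboratory tests only, so no such bias is shown for vital signs or ECG. Protocol 8.2.4 also generally excludes findings tied to the underlying disease from clinical significance, which narrows the concern for TSH.

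All four points stand and limit the concern. They do not remove it. Adverse event tables carry event terms rather than values, so they cannot restore a mean, maximum or change from baseline. Nor do the PCS tables help for parameters without a limit or for abnormalities below it.

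**Conclusion.** The point holds as a minor one. Followed as written, the two documents let a resolved and normally off-treatment repeat replace the scheduled final laboratory value, with a predictable pull toward no change in the EOT mean, maximum and change from baseline. At earlier visits this happens only when the repeat falls in the same window.

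The size cannot be derived from the documents. The range of 0.007 to 0.282 × ULN rests on assumed counts and values and on every repeat settling at 1 × ULN. A median would barely move with so few participants, whereas a maximum can change outright. The conclusion also assumes that repeats after Visit 7 reach the study database as post-baseline assessments.

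The loss is confined to descriptive laboratory summaries. It matters most for TSH, thyroid hormones and HbA1c, and for significant values below the Table 11-1 limits. SAP 16.3 governs no primary or secondary efficacy test.

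**What to change.** In SAP 16.3, define the EOT value for descriptive summaries of safety laboratory parameters as the scheduled Visit 7 or Early Termination result. In SAP 16.2, for the same summaries, use the scheduled result at earlier visits. Allow a repeat to substitute only when the scheduled result is missing or technically invalid. Follow-up repeats can be shown separately.

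Keep all post-baseline values for PCS determination and listings, as already planned. Leave the rule for the TSH efficacy endpoint unchanged, and word the SAP 16.2 change so that it applies to safety laboratory summaries only. The protocol's repeat testing is not touched.

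The cost is one SAP sentence and one programming rule, with no extra data.

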### **16.4 MISSING DATE OF THE LAST DOSE OF STUDY TREATMENT**

When the date of the last dose of the double-blind investigational product is missing, all efforts should be made to obtain the date from the Investigator. If it is still missing after all efforts have been made, the last diary date will be used as the last dose date.

### **16.5 MISSING SEVERITY ASSESSMENT FOR ADVERSE EVENTS**

If severity is missing for an AE that started before the date of the first dose of double-blind investigational product, an intensity of mild will be assigned. If severity is missing for an AE that started on or after the date of the first dose of double-blind investigational product, an intensity of severe will be assigned. The imputed values for severity assessment will be used for the incidence summary; the values will be shown as missing in the data listings.

### **16.6 MISSING CAUSAL RELATIONSHIP TO STUDY TREATMENT FOR ADVERSE EVENTS**

If the causal relationship to the investigational product is missing for an AE that started on or after the date of the first dose of double-blind investigational product, a causality of yes will be assigned. The imputed values for causal relationship to double-blind treatment will be used for the incidence summary; the values will be shown as missing in the data listings.

### **16.7 MISSING DATE INFORMATION FOR ADVERSE EVENTS**

The following imputation rules apply to cases in which the start date is incomplete (i.e., partial missing) for AEs.

### **Missing day and month**

- If the year is the same as the year of the date of the first dose of double-blind investigational product, then the day and month of the date of the first dose of double-blind investigational product will be assigned to the missing fields.
- If the year is prior to the year of the date of the first dose of double-blind investigational product, then December 31 will be assigned to the missing fields.
- If the year is after the year of the date of the first dose of double-blind investigational product, then January 1 will be assigned to the missing fields.

### **Missing month only**

- The day will be treated as missing and both month and day will be replaced according to the above procedure.

### **Missing day only**

- If the month and year are the same as the month and year of the date of the first dose of double-blind investigational product, then the date of the first dose of double-blind investigational product will be assigned to the missing day.
- If either the year is before the year of the date of the first dose of double-blind investigational product or if both years are the same but the month is before the month of the date of the first dose of double-blind investigational product, then the last day of the month will be assigned to the missing day.
- If either the year is after the year of the date of the first dose of double-blind investigational product or if both years are the same but the month is after the month of the date of the first dose of double-blind investigational product, then the first day of the month will be assigned to the missing day.

If the stop date is complete and the imputed start date as above is after the stop date, the start date will be imputed by the stop date.

If the start date is completely missing and the stop date is complete, then the following algorithm is used to impute the start date:

- If the stop date is on or after the date of the first dose of double-blind investigational product, the date of the first dose of double-blind investigational product will be assigned to the missing start date.
- If the stop date is before the date of the first dose of double-blind investigational product, the stop date will be assigned to the missing start date.

## 16.8 MISSING DATE INFORMATION FOR PRIOR OR CONCOMITANT MEDICATIONS

For prior or concomitant medications, excluding rescue medications, incomplete (i.e., partly missing) start dates and/or stop dates will be imputed. When the start date and the stop date are both incomplete for a participant, the start date will be imputed first.

### 16.8.1 Incomplete Start Date

The following rules will be applied to impute the missing numeric fields for an incomplete prior or concomitant medication start date. If the stop date is complete (or imputed) and the imputed start date is after the stop date, the start date will be imputed using the stop date.

#### Missing month and day

- If the year of the incomplete start date is the same as the year of the first dose of study treatment, the month and day of the first dose of study treatment will be assigned to the missing fields
- If the year of the incomplete start date is before the year of the first dose of study treatment, *December 31* will be assigned to the missing fields
- If the year of the incomplete start date is after the year of the first dose of study treatment, *January 1* will be assigned to the missing fields

#### Missing month only

- If only the month is missing, the day will be treated as missing and both the month and the day will be replaced according to the above procedure

#### Missing day only

- If the month and year of the incomplete start date are the same as the month and year of the first dose of study treatment, the day of the first dose of study treatment will be assigned to the missing day
- If either the year of the incomplete start date is before the year of the date of the first dose of study treatment or if both years are the same but the month of the incomplete start date is before the month of the date of the first dose of study treatment, the last day of the month will be assigned to the missing day.
- If either the year of the incomplete start date is after the year of the date of the first dose of study treatment or if both years are the same but the month of the incomplete start date is after the month of the date of the first dose of study treatment, the first day of the month will be assigned to the missing day

### 16.8.2 Incomplete Stop Date

The following rules will be applied to impute the missing numeric fields for an incomplete prior or concomitant medication stop date. If the date of the last dose of study treatment is missing, impute it as described in Section 16.4. If the imputed stop date is before the start date (imputed or non-imputed start date), the imputed stop date will be equal to the start date.

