## **8.0**

## **DEMOGRAPHICS AND OTHER BASELINE CHARACTERISTICS**

Demographic parameters (e.g., age, race, ethnicity, sex) and other baseline characteristics (weight, BMI) will be summarized in total and by treatment group for the four analysis populations (ITT and ITT-T3 Populations, Safety and Safety-T3 Populations).

Abnormalities in participants' medical and surgical histories will be coded using the *Medical Dictionary for Regulatory Activities*, version 21.1 or newer. The number and percentage of participants with abnormalities in medical and surgical histories in each system organ class and preferred term will be summarized by treatment group for the ITT and ITT-T3 Populations.

*Prior medication* is defined as any medication started before the date of the first dose of double-blind study treatment. *Concomitant medication* is defined as any medication taken on or after the date of the first dose of double-blind study treatment. Any prior medications started more than 30 days before the date of the first dose of double-blind study treatment and any concomitant medications started after the date of the last dose of double-blind study treatment will not be presented in the summary tables, but will be included in the participant data listings.

Both prior and concomitant medication use will be summarized by the number and proportion of participants in each treatment group for the ITT and ITT-T3 Populations. The *WHO Drug Dictionary*, Version B2 March 2017 or newer, will be used to classify prior and concomitant medications by WHO Drug Anatomical/Therapeutic/Chemical category and drug preferred name. Multiple medications used by a participant will only be counted once for the coded drug preferred name or therapeutic class.

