### **Missing day only**

- If the month and year of the incomplete stop date are the same as the month and year of the last dose of study treatment, the day of the last dose of study treatment will be assigned to the missing day
- If either the year of the incomplete stop date is before the year of the date of the last dose of study treatment or if both years are the same but the month of the incomplete stop date is before the month of the date of the last dose of study treatment, the last day of the month will be assigned to the missing day
- If either the year of the incomplete stop date is after the year of the date of the last dose of study treatment or if both years are the same but the month of the incomplete stop date is after the month of the date of the last dose of study treatment, the first day of the month will be assigned to the missing day.

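### SAP 16.8.1 and 16.8.2 settle the same date conflict in opposite ways, so for one partial-date pattern a medication that ended before treatment is counted as concomitant; separately, the adverse-event cap in 16.7 ignores partial stop dates.

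*SAP*

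**What the plan says.** **Medications (SAP 16.8).** The order is fixed: "When the start date and the stop date are both incomplete for a participant, the start date will be imputed first". For a start with month and day missing, in the year of first dose, "the month and day of the first dose of study treatment will be assigned to the missing fields" (16.8.1). For a stop with only the day missing, in a month before that of the last dose, "the last day of the month will be assigned to the missing day" (16.8.2).

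Two sentences then deal with a start that falls after the stop:

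- SAP 16.8.1: "If the stop date is complete (or imputed) and the imputed start date is after the stop date", the start is replaced by the stop.
- SAP 16.8.2: if the imputed stop is earlier than the start, whether or not that start was itself imputed, "the imputed stop date will be equal to the start date".

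SAP 8.0 classifies by the first-dose date. A prior medication "is defined as any medication started before the date of the first dose of double-blind study treatment"; a concomitant medication "is defined as any medication taken on or after the date of the first dose of double-blind study treatment".

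**Adverse events (SAP 16.7).** A start with only the year known, equal to the first-dose year, becomes the first-dose date. The cap on that start is conditional: "If the stop date is complete and the imputed start date as above is after the stop date", the stop date is used. No rule covers a partly recorded stop, and adverse-event stop dates are not imputed. SAP 11.1 counts an event as treatment-emergent if it began on or after the first-dose date.

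**The concern.** A recorded stop month is data. A start filled in from the first-dose date is a convention. Where the two conflict, the convention should give way, and the SAP does this when the stop date is complete. Under 16.8.2 the reverse happens when the stop is partial: the filled-in start overrides a month that the site recorded, and a medication that had ended before treatment appears as taken on Day 1. The adverse-event rule produces a similar error by another route, because a partial stop cannot cap the start at all.

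At stake are the prior and concomitant medication summaries and the TEAE counts, which could contain items that the database shows had ended before dosing.

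**Working it through.** The plan gives no figure to reproduce. The check applies the rules in the stated order.

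**Inputs.** The rules are those above. The dates are assumed for illustration: first dose FD = 10 Sep 2020, last dose LD = 1 May 2021, recorded start 2020 (year only), recorded stop Aug 2020 (no day).

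**Medication, in the order of SAP 16.8**

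1. Start: year = year of FD and month missing, so start = FD = 10 Sep 2020.
2. The 16.8.1 check: the stop is not complete and has not yet been imputed, so nothing happens.
3. Stop: Aug 2020 is before the month of LD, so stop = 31 Aug 2020.
4. The 16.8.2 check: 31 Aug < 10 Sep, so stop = start = 10 Sep 2020.
5. Class under SAP 8.0: start < FD is false, so not prior; taken on FD, so concomitant.

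| Rule applied to the conflict | Start | Stop | Class |
|---|---|---|---|
| 16.8.2 (operative in the stated order) | 10 Sep 2020 | 10 Sep 2020 | concomitant, not prior |
| 16.8.1, if applied after the stop is imputed | 31 Aug 2020 | 31 Aug 2020 | prior only |
| Stop recorded in full, e.g. 25 Aug 2020 | 25 Aug 2020 | 25 Aug 2020 | prior only |

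31 Aug is 10 days before first dose, inside the 30-day limit that SAP 8.0 sets for showing prior medications in the tables. The record therefore leaves the prior table and enters the concomitant table.

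**Which patterns fail.** Consider partial pairs whose recorded stop is certainly before first dose.

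- Start month missing, first-dose year, stop month earlier in that year: start = FD and imputed stop < FD, so 16.8.2 always gives stop = FD. Always misclassified.
- Start month recorded: for a feasible record the start month is no later than the stop month, so the imputed start is not after the imputed stop. Correct.
- Start in an earlier year: the imputed start is at latest 31 December of that year, before FD, so the stop is never moved to FD or later. Correct class.

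An enumeration confirms this. It used start and stop years 2019 and 2020; first dose on 15 Feb, 15 Jun or 15 Nov 2020; and treatment of 210 or 336 days. Of 1,208 feasible pairs, 32 were misclassified, all in the first pattern: (1 + 5 + 10 earlier stop months) × 2 lengths = 32. The other 1,208 − 32 = 1,176 were classified correctly. Resolving the conflict as in 16.8.1 gave 0 of 1,208. These are counts of date patterns, not expected frequencies.

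**Adverse event with the same dates.** Start 2020 becomes 10 Sep 2020. The stop Aug 2020 is not complete, so the cap does not apply. Onset = FD, so the event is a TEAE. With a complete stop of 25 Aug 2020 the start would be 25 Aug and the event would not be a TEAE. In the enumeration the adverse-event rule failed in the same 32 patterns and no others.

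**Feasibility.** Protocol 6.5.1 and 8.3.1 start recording at consent, and SAP 4.1 limits screening to 3 weeks. Taking 21 days, 10 Sep − 21 days = 20 Aug, so a stop between 20 and 31 Aug lies within the recording period. More generally, the window reaches the preceding month of the same year only when first dose falls on days 1 to 21 of February to December: 11 × 21 = 231 of 366 dates in 2020, or 63%.

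**The case against.** **The order already gives one answer.** With the start imputed first, the words in 16.8.1 about an imputed stop never take effect, so a reader who infers that the SAP equally licenses two classifications goes too far. This stands. What remains is that the two sentences contradict each other, the SAP does not say which prevails, and the stated order selects the one that gives the wrong result.

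**Partial dates are mostly handled well.** A reader might infer that the rules fail whenever both dates are partial. They do not: the failure is confined to one pattern. Nor is the adverse-event gap the same mechanism, since no adverse-event stop date is moved; the cap simply does not reach partial stops.

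**Counting more events is cautious.** SAP 16.5 and 16.6 set missing severity to severe and missing causality to yes, and an extra TEAE errs in the same direction. That suits dates that are truly unknown. Here the recorded month rules out an event or use on treatment, and the SAP already accepts that logic for complete stops.

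**Such records will be rare.** This also stands. Recording runs from consent, screening is short, and concomitant medication is asked about at every visit (Protocol 6.5). A year-only start for an adverse event with onset in those weeks would be unusual; a year-only start for an existing medication is more plausible.

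**Conclusion.** Wrong as written, and minor. For a start with its month missing in the first-dose year and a stop month recorded earlier in that year, SAP 16.8.2 turns a finished medication into a concomitant one, and SAP 16.7 turns a finished event into a TEAE. Every record of that pattern is affected. The other partial pairs with a stop certainly before first dose are classified correctly.

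The number of such records is not given and should be small. The calendar dates are assumed, but the result depends only on the pattern. The medication result rests on following the SAP's stated order. Nothing supports reading this as a threat to the efficacy conclusions: the TSH endpoints use none of these dates.

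**What to change.** **SAP 16.8.2.** Replace the last sentence of the opening paragraph with: *If the imputed stop date precedes an imputed start date, the start month is missing, and the stop month and year are recorded, set the start date to the imputed stop date. Otherwise, if the imputed stop date precedes the start date, set the stop date to the start date.* Align 16.8.1 by keeping its check for complete stops and referring to 16.8.2 for partial ones.

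The conditions on recorded months are needed. A rule that always moved an imputed start to the imputed stop would create the reverse error. Take first dose 10 Sep 2020, last dose 5 Jan 2021, start Mar 2021, stop 2021. The start is imputed as 1 Mar 2021 and the stop as 5 Jan 2021. Moving the start to 5 Jan would override a recorded start month and bring a medication begun after the last dose into the concomitant table, from which SAP 8.0 keeps it out. Under the wording above the start month is recorded, so the stop moves to 1 Mar 2021, as it does now.

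**SAP 16.7.** Extend the cap to stop dates with a recorded month and year, using the last day of that month as the latest allowed imputed start.

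All 32 failing patterns meet the new conditions, so they are corrected. The cost is a few sentences in the SAP and a small programming change, with no new data.
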